10. EFFICACY ANALYSES

The efficacy endpoints for this study are secondary analyses and will be based on the safety population.

10.1 Efficacy Variables

Efficacy will be assessed based on a series of ophthalmologic assessments performed at specified intervals, including BCVA, LLMT, CST, and KVF testing.

10.1.1 Secondary Efficacy Assessments

Secondary efficacy endpoints include mean change at Month 6 and Month 12 in the following assessments: BCVA, to be measured with the electronic visual acuity testing algorithm (E-ETDRS); LLMT scored by critical illumination level [CIL]); KVF assessed by Octopus 900 kinetic visual field testing, and peak CS measured with gratings in the Beethoven system.

- BCVA (E-ETDRS) (performed at the clinical site): BCVA will be tested at scheduled time points in both eyes in all subjects. Visual acuity will be measured with the E-ETDRS for eyes with vision better than 20/800. The measurements will be taken using a single line testing strategy with two measurements per eye at each study visit. In the event that the two measurements differ by more than seven letters, then a third measurement will be taken. For any individual eye that cannot be tested with the E-ETDRS, a score of zero letters will be used.
- LLMT (performed at jCyte Central Testing Facility): In general, the LLMT will consist of differing but structurally similar configurations of a relatively short courses (e.g. arrows on a printed floor mat) with ten obstacles, of various sizes. Subject testing consists of walking through several configurations each at a different illumination level as a test of mesopic visual function. Each test is videotaped and scored for speed and accuracy (number of errors) by masked independent trained graders and a score, the Critical Illumination level (CIL), is derived from the illumination level at which a significant drop in functional performance is observed (slow walking speed and increase in errors).

For subjects assessed during the baseline testing who have an estimated monocular CIL of 1 lux or lower (near normal vision), they will be tested with that eye on both a high contrast (black and white) and a low contrast version (either 25% or 10% light grey arrows) at Baseline. At follow-up visits, the same low contrast version will be used for that eye at each later visit. A larger range of testing improvement should occur in the low contrast version, allowing for greater test sensitivity (i.e., preventing a ceiling effect) if the subject's vision improves with treatment. If a subject can only perform the high contrast version, then each eye and both eyes together will be assessed.

- Kinetic Visual Field Testing (performed at jCyte Central Testing Facility): The Octopus 900 will be used for KVF testing using a specified target of V4e for subjects with a more severely impaired visual field (<10,000deg²) and a target of III4e and I4e for better seeing subjects (>10,000deg²). Target size will be selected based on Baseline visit for each eye separately. Whatever target size(s) is/are selected, the same size will be used throughout the study on that particular eye.
- Contrast Sensitivity Test (performed at jCyte Central Testing Facility): A CST test measures the ability of a subject to distinguish between finer and finer increments of light versus dark (contrast). Contrast provides critical information about edges, borders, and variations in luminance. CST is correlated to performance on many real world tasks and tests that generate a curve or multiple sensitivity thresholds at varying grating sizes

(spatial frequency [SF]) provide an in-depth view of functional vision. Using the Beethoven System, multiple thresholds and varying spatial frequencies creating a curve will be measured monocularly and the peak of the curve will be compared over time. Each spatial frequency is tested up to seven times (thresholds) so the mean threshold at the peak CST for each eye will be compared over time.

For each eye, threshold CST values will be recorded for spatial frequencies from the following range: 0.25, 0.5, 1.0, 2.0, 4.0, 8.0 and 16.0 (not all frequencies will be tested for each eye for each subject). If a subject can test at more than one target size (or SF), then at least three SFs will be tested with multiple trials at each to determine the mean thresholds for each SF.

10.1.2 Exploratory Assessments

Subjects may be asked to undergo additional testing at the jCyte central testing facility to assess the characteristics of the jCell aggregate inside the eye (size and structure) and retinal sensitivity following treatment. These are exploratory assessments, and any/all may be discontinued if they are determined to be difficult to conduct or the results appear to be of little value in understanding the course of the injected cells and/or changes in retinal sensitivity over time.

- **B-Scan (performed at jCyte Central Testing Facility):** B-scan ultrasound uses highfrequency sound waves to obtain measurements and produce detailed images of the eye. In the area of the typical intravitreal (IVT) injection site, two or more probe directions (perpendicular to the corneal surface and inferotemporal) will be used to locate jCells. This test may provide information regarding the location of the injected cells and the general size of the cell clusters at different time points post-treatment.
- Ultrasound Biomicroscopy (UBM) (performed at jCyte Central Testing Facility): With the same ultrasound instrument as for B-scans, but using a different probe for UBM, high-frequency high-resolution images of the cross-sectional anterior chamber can be acquired. UBM will be used to explore a more thorough volume estimation by ultrasound imaging of the jCell aggregate over time.
- Slit lamp biomicroscopy with gonioscopy lens & photography (performed at jCyte Central Testing Facility): Binocular slit lamp biomicroscopy provides a stereoscopic magnified view of eye structures, enabling general anatomical exploration of the jCell aggregate over time. When combined with a gonioscopy contact lens (three-mirror lens with gel between the lens and cornea), a greater viewing angle into the anterior vitreous behind the iris to view and photograph/videograph jCells may be achieved. Photography and/or video recording with or without the gonioscopy lens will be used as a means to explore the physical description of the jCell aggregate over time.
- **SD-Optical Coherence Topography (performed at jCyte Central Testing Facility):** Standard spectral domain optical coherence tomography (SD-OCT) imaging is primarily used for image segmentation of the posterior segment and often specifically the macular

region. However, it may be possible to capture a cross-section of jCell using novel variants of OCT imaging in order to understand cell morphology. In order to image anterior vitreous or peripheral retinal locations where injected jCells may be located, an OCT instrument for anterior and posterior segment imaging may be used.

• Full-Field Scotopic Threshold Test (FST) (performed at jCyte Central Testing Facility): Full-field stimulus threshold testing (FST) using light emitting diode (LED)-based ganzfeld stimulator (Colordome, Diagnosys LLC, Littleton, MA) can provide an estimation of which photoreceptor type (rod vs cone) is predominantly mediating light sensitivity. With serial FST assessments, changes in the retinal sensitivity of rods vs. cones in response to jCell therapy will be assessed. Blue and red stimuli can be used for testing monocularly under dark-adapted conditions.

The study protocol also lists A-scan ultrasound as an exploratory assessment. However, this assessment was not included in the final list of study assessments and was not performed on any patients.

10.2 Baseline Values

For the efficacy variables, apart from BCVA, the baseline value of an assessment will be the value collected at the Baseline visit. For BCVA, the value collected at the Day 0 visit will be used as the baseline value for analysis. If for any reason a subject does not have a BCVA assessment at Day 0, then the value collected at the Baseline visit will be used as the baseline value for analysis.

Subjects who cannot perform CS or KVF at Baseline will not be compared at later visits for that assessment. For the two secondary endpoints of BCVA and LLMT, 0 letters will be used for BCVA and -1 for the scale score for LLMT if the subject attempts but is unable to meet the minimum score for the assessment. This will be done during the programming of the analysis datasets and will not be done by the site/testing facility.

10.3 Handling of Dropouts or Missing Data

Subjects with missing data (no assessment) at Baseline will be considered non-evaluable for analysis of that assessment, except for the two secondary endpoints of BCVA and LLMT. If a subject attempts but is unable to meet the minimum score for the assessment at any visit, a value of 0 letters will be used for BCVA and -1 for the scale score for LLMT. This will be done during the programming of the analysis datasets and will not be done by the site/testing facility.

Other than what is noted above, any other data that is not obtained due to lack of assessment or missed visits will not be imputed.

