9.2 Efficacy Analyses (Secondary Endpoints)

Efficacy endpoints are secondary analyses and include assessment of change in BCVA, mobility, contrast sensitivity, and visual fields.

BCVA will be measured with the electronic visual acuity testing algorithm (E-ETDRS) and will be assessed by comparison of the mean change in number of letters correct from baseline.

Mobility will be assessed by comparison of mean change in CIL from baseline, unilaterally and bilaterally.

Descriptive statistics will be used to tabulate and summarize study outcomes. The baseline results of clinical examinations of the injected eye serve as controls for the injected eye for the purpose of reporting changes in visual parameters from baseline to 6 or 12 months post-treatment. Results of testing of the non-tested eye will also be described. Continuous variables will be summarized descriptively (sample size, mean standard deviation and error,

minimum and maximum). Discrete variables will be summarized by frequency or percentage, and analyzed with non-parametric statistics.

Subjects who cannot perform a specific visual test at baseline will be assigned the lower limit of detection, if applicable, for the relevant test. Subjects with missing data (no assessment) at baseline will be considered non-evaluable for analysis of that assessment.

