11.1.2 Low Luminance Mobility Test (LLMT)

Low luminance mobility will be assessed by comparison of mean change in CIL scale scores from baseline. CIL scale scores will be summarized in Study Eye and Both Eyes at Baseline, Month 6 and Month 12. In addition, change from baseline will also be summarized using summary statistics for each post-baseline time point.

CIL scores will be converted to a scale score of -1 (cannot pass at the brightest light level) to 13 (does not slow even with room lights off). Conversion of CIL lux values to scale scores are included in the following table:

CIL (Lux)	Lights off	0.12	0.25	0.5	1.0	2.0	4.0	8.0	16	32	63	125	250	500	No Pass
Scale Score	13	12	11	10	9	8	7	6	5	4	3	2	1	0	-1

Subjects who cannot perform mobility testing at Baseline will be considered to have a scale score of -1 for CIL. The assignment of a -1 CIL scale score will be done during the programming of the analysis datasets.

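### SAP 10.3 exempts BCVA and LLMT from the missing-baseline rule, contrary to Protocol 9.2, and gives an unassessed baseline no stated value

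*SAP*

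**What the plan says.** - Protocol 9.2 separates two cases. A subject who cannot perform a test at baseline gets the lower limit of detection, where one applies. For the other case, "Subjects with missing data (no assessment) at baseline will be considered non-evaluable for analysis of that assessment". No test is excepted.
- SAP 10.3 repeats the second rule but makes such subjects "non-evaluable for analysis of that assessment, except for the two secondary endpoints of BCVA and LLMT".
- SAP 10.2 gives the floor (0 letters for BCVA, -1 for LLMT) "if the subject attempts but is unable to meet the minimum score for the assessment". SAP 10.3 extends the same condition to every visit. It then closes, subject to what it has already noted, by saying that "any other data that is not obtained due to lack of assessment or missed visits will not be imputed".
- SAP 11.1.2 has no attempt condition: "Subjects who cannot perform mobility testing at Baseline will be considered to have a scale score of -1 for CIL". SAP 10.1.1 likewise scores zero letters for an eye that cannot be tested with the E-ETDRS.
- SAP 11.1.3 (CST) and 11.1.4 (KVF) each state that a completely missing baseline is not evaluable. SAP 11.1.1 (BCVA) and 11.1.2 (LLMT) have no such sentence.
- SAP section 15 lists two changes from the protocol: the new name of the mobility test and the dropped A-scan.

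**The concern.** The exception in SAP 10.3 attaches to subjects with no assessment, not to subjects who tried and failed. Taken literally, it keeps a subject with no LLMT or BCVA baseline in the change analysis without saying what the baseline is. The only substitute values the SAP offers for these tests are floors, and two sections state the floor without requiring an attempt. SAP 10.2 and 10.3 leave the assignment to whoever programs the analysis datasets, so the wording decides the result.

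A floor used in place of an unmeasured baseline cannot make a subject's change look worse than it was. Missed follow-up values are not imputed, and the study has a single arm, so nothing offsets an upward shift. LLMT is the more exposed test. Protocol Table 2 schedules one measurement before injection, at the sponsor's testing facility, and the SAP names no fallback.

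**Working it through.** **1. Compare the rules by case.**

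| Situation at baseline | Protocol 9.2 | SAP 10.2 and 10.3 | SAP 10.1.1, 11.1.1, 11.1.2 |
|---|---|---|---|
| Attempted, minimum not met | Not named separately | Floor: 0 letters or -1 | Floor |
| Could not be tested because of vision | Lower limit of detection, where applicable | No value, since there was no attempt | Floor: zero letters or -1 |
| Not assessed for another reason (missed visit, injury, equipment) | Non-evaluable | BCVA and LLMT exempted from non-evaluable; no value given | No rule in terms; the sentence used for CST and KVF is absent |

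The third row is the defect. The SAP removes the protocol's rule for these two tests and puts nothing in its place.

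**2. Inputs for the size.** The plan has no figure of its own to reproduce: SAP section 5 sets N at 25 to 30 by availability, and no effect size or SD is given.
- LLMT scale: "CIL scores will be converted to a scale score of -1 (cannot pass at the brightest light level) to 13", with higher scores better (SAP 11.1.2).
- Change = post-baseline value minus baseline value (SAP Appendix A).
- Assumed, not in the documents: the true score s, the true letter score L, the number k of affected subjects, no real change in those subjects, and all N subjects contributing to the mean.

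**3. LLMT.** False change per affected subject = s - (-1) = s + 1. Shift in the mean = k(s + 1)/N.

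| s | False change | Shift, N = 30, k = 1 | Shift, N = 25, k = 1 |
|---|---|---|---|
| 0 (500 lux) | 1 | 1/30 = 0.03 | 1/25 = 0.04 |
| 6 (8 lux) | 7 | 7/30 = 0.23 | 7/25 = 0.28 |
| 9 (1 lux) | 10 | 10/30 = 0.33 | 10/25 = 0.40 |
| 13 (lights off) | 14 | 14/30 = 0.47 | 14/25 = 0.56 |

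Two affected subjects at s = 6 give 14/30 = 0.47 to 14/25 = 0.56 steps.

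**4. BCVA.** False change = L - 0 = L. For an assumed L of 20 to 80 letters, one affected subject shifts the mean by 20/30 = 0.67 to 80/30 = 2.67 letters at N = 30, or 20/25 = 0.80 to 80/25 = 3.20 at N = 25. This needs the Day 0 and Baseline-visit values both to be absent, because SAP 10.2 falls back from one to the other.

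**5. Attempt-only reading.** If the floor is given only after a failed attempt, an unassessed baseline has no value, change cannot be computed, and the shift is 0.

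**The case against.** A reader might infer that the SAP directs an unmeasured baseline to be set to the floor, and so builds a false improvement into LLMT. The documents do not support that. SAP 10.2 and 10.3 tie the floor to an attempt. The closing sentence of 10.3 bars imputation for lack of assessment or missed visits, and the only imputation noted above it is the floor after a failed attempt. Both documents also distinguish being unable to perform a test from not being assessed (Protocol 9.2, SAP 11.1.4). SAP 11.1.2 defines -1 as failing to pass at the brightest level. In SAP 10.1.1, the zero-letter rule follows a statement that the E-ETDRS is for eyes better than 20/800, which points to poor vision and not to a missed test. The exception may have been meant only to introduce the attempt-and-fail rule in the next sentence.

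All of this stands as the more natural reading of intent, and it means that no section expressly floors an unattempted baseline. It does not repair the text. An attempted and failed test is not a missing assessment, so an exception meant for it is attached to the wrong category. The 10.3 bar opens with a carve-out and so does not clearly override the exception. The missing sentence in 11.1.1 and 11.1.2 matches the exception, so the gap is not confined to one clause.

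Two further points hold. SAP section 11 plans no formal efficacy evaluation, and LLMT values are listed by subject, which would help expose a -1 with no test behind it.

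**Conclusion.** The point holds as a wrong stated rule, with a bias that is possible but not directed. The exception in SAP 10.3 contradicts Protocol 9.2, is undeclared in section 15, and leaves unassessed BCVA and LLMT baselines evaluable with no value. A false improvement arises only if the exception is combined in programming with the unconditioned floor in 11.1.2 or 10.1.1. In that case the LLMT mean change rises by (s + 1)/N per affected subject: 0.23 to 0.28 steps for an assumed s of 6, and 0.03 to 0.56 over s = 0 to 13 and N = 30 to 25. Otherwise the effect is zero. The documents do not show whether any subject is affected. The BCVA risk is small because of the fallback. Only secondary, descriptive summaries are at stake; the primary safety objective is untouched. A correction is still worthwhile, because any error would run in one direction in a single-arm study and the remedy costs almost nothing.

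**What to change.** 1. In SAP 10.3, delete the exception for BCVA and LLMT.
2. In SAP 10.3, 11.1.1 and 11.1.2, state that the floor applies only when the test was attempted and the minimum was not met, or when it could not be done because of the subject's vision. The second limb is needed to keep the protocol's lower-limit rule. Align the zero-letter sentence in 10.1.1 with this.
3. State that a baseline not assessed for any other reason (missed visit, injury, equipment) is missing and non-evaluable for change, for every test, as in Protocol 9.2.
4. Report the number of baselines set to the floor, by test.

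The cost is a few sentences and one count. The downside is that any subject with no baseline drops out of the change summary for that test. The documents do not show whether the database has been locked. If it has, the rule actually used and the count of floored baselines can be given in the CSR, where SAP section 1 already places deviations from the plan.

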10.4 Interim Analysis and Data Monitoring

No interim analysis is planned for this study.

10.5 Examination of Subgroups

There are no planned subgroup analyses for this study.

10.6 Multiple Comparison/Multiplicity

No adjustments for multiplicity will be made in this study.

10.7 Multicenter Studies

No analyses are planned to compare differences in the response by center.

11. METHODS OF EFFICACY ANALYSIS

No formal efficacy evaluation will be performed as the study is primarily a safety study. However, secondary endpoints will be observed over time and summarized in tables. These assessments include BCVA as assessed at the clinical site at all visits, as well as LLMT, CST, and KVF at Baseline and at Month 6 and Month 12 as assessed at the jCyte central testing facility.

All efficacy analyses will be based on the safety population.

11.1 Efficacy Analyses

11.1.1 Best Corrected Visual Acuity (BCVA)

BCVA will be analyzed using summary statistics of the average number of letters correct at each time point. Separate tables will be created for the Study Eye and the Non-Study Eye. Change from baseline will also be summarized using summary statistics for each post-baseline time point. Subjects who cannot see any letters on the chart at Baseline will be considered to have a 0 letter score. The assignment of a 0 letter score will be done during the programming of the analysis datasets and will not be done by the site/testing facility.

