3.2 Endpoints

3.2.1 Efficacy Endpoints

Efficacy will be assessed as secondary endpoints in this study and will include for all subjects vision parameters of Best Corrected Visual Acuity (BCVA) as assessed at the clinical site at all visits, as well as mobility (maze navigation), contrast sensitivity (CS), and visual fields (VF) at baseline and at six and 12 months after treatment as assessed at the jCyte low vision facility.

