3.2.2 Safety Endpoints

The main criteria that will be used to assess safety include:

- Incidence and severity of treatment-emergent adverse events (TEAE)
- Safety visual assessments: slit lamp and fundus exam, IOP

Blood samples will be collected from subjects at baseline and at designated times post-treatment to assess immunogenicity of the injected cells (PRA, DRA).

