6. GENERAL ANALYSIS CONSIDERATIONS

The statistical analyses will be reported using summary tables and listings (TLs). The International Council for Harmonisation of Technical Requirements for Pharmaceuticals for Human Use (ICH) numbering convention will be used for all TLs.

Continuous variables will be summarized by presenting the number of observations, means, standard deviations (SDs), medians, minimums, and maximums.

Categorical variables will be summarized by presenting counts and percentages of subjects in corresponding categories. Percentages for missing values are omitted and do not account for the percent calculation of other categories. Percentages are based on the total category count excluding the missing category if not otherwise mentioned. In certain tables (e.g. adverse events [AEs]), the total number of subjects is used as the denominator. Footnotes will specify the percent basis in those cases.

All summary tables will be presented using the single jCell treatment group.

Treatment will be analyzed as actually performed rather than as planned. Any subjects who do not receive the full dose of study drug will be analyzed with those who do receive the full dose of study drug.

Individual subject data obtained from the eCRFs and any derived data will be presented by subject in data listings.

The analyses described in this plan are considered a priori, in that they have been defined prior to database lock.

Any analyses performed after database lock will be considered post hoc and exploratory. Post hoc analyses will be labeled as such on the output and identified in the CSR.

All analyses and tabulations will be performed using SAS[®] statistical software, version 9.4 or higher (SAS Institute Inc). Tables and listings will be presented in RTF format.

The process for SAS program validation and quality control (QC) for programs and outputs is documented in the Synteract working instruction "SAS Programming Quality Control".

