13. SAFETY ANALYSES

The primary endpoint of this study is to obtain safety profiles for reinjection of jCell. The safety analyses of AEs and laboratory parameters will include descriptive statistics. Summaries of AEs will be generated by type (AE or SAE), body system and PT, severity, and relationship to study product.

All safety analyses will be based on the safety population.

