14.3.3.5	Intraocular Pressure (IOP): Study Eye	Safety Population	
14.3.3.6	Intraocular Pressure (IOP): Non-Study Eye	Safety Population	
14.3.3.7	Clinical Vitreous Exam: Study Eye	Safety Population	
14.3.3.8	Categorical Analysis of Optical Coherence Tomography (OCT)	Safety Population	
14.3.4	Other Safety Data		
14.3.4.1	Hematology	Safety Population	
14.3.4.2	Chemistry	Safety Population	
14.3.4.3	Vital Signs	Safety Population	· · · · · · · · · · · · · · · · · · ·

Abbreviations: ECG=electrocardiogram; E-ETDRS= electronic visual acuity testing algorithm; FA=full analysis; ICH=International Council for Harmonisation of Technical Requirements for Pharmaceuticals for Human Use; PP=per-protocol; TEAE=treatment-mergent adverse events

Index of Sectior	ı 16.2		
ICH Listing Number	Listing Title	Analysis Set	Comments
16.2	Subject Data Listings		
16.2.1	Discontinued Subjects		
16.2.1.1	Subject Disposition	All Subjects	
16.2.2	Protocol Deviations		
16.2.2.1	Protocol Deviations	All Subjects	
16.2.3	Demographic Data		
16.2.3.1	Demographics and Baseline Characteristics	Safety Population	
16.2.3.2	Medical History	Safety Population	
16.2.3.3	Ocular Medical History	Safety Population	
16.2.3.4	Prior and Concomitant Medications	Safety Population	
16.2.4	Individual Efficacy Response Data		
16.2.4.1.1	Best Corrected Visual Acuity (E-ETDRS): Study Eye	Safety Population	
16.2.4.1.2	Best Corrected Visual Acuity (E-ETDRS): Non-Study Eye	Safety Population	
16.2.4.2.1	Low Luminance Mobility Test (LLMT): Study Eye	Safety Population	
16.2.4.2.2	Low Luminance Mobility Test (LLMT): Both Eyes	Safety Population	
16.2.4.3.1	Kinetic Visual Fields (KVF): Study Eye	Safety Population	
16.2.4.3.2	Kinetic Visual Fields (KVF): Non-Study Eye	Safety Population	
16.2.4.4.1	Contrast Sensitivity Test (CST): Study Eye	Safety Population	
16.2.4.4.2	Contrast Sensitivity Test (CST): Non-Study Eye	Safety Population	
16.2.5	Compliance and/or Drug Concentration Data		
16.2.5.1	Study Drug Administration	Safety Population	
16.2.6	Adverse Events		
16.2.6.1	Adverse Events	Safety Population	
16.2.6.2	Serious Adverse Events	Safety Population	
16.2.6.3	Related Adverse Events	Safety Population	
16.2.7	Ophthalmic Safety Examinations		
16.2.7.1.1	Slit Lamp Exam: Study Eye	Safety Population	
16.2.7.1.2	Slit Lamp Exam: Study Eye -Vitreous Findings	Safety Population	

CONFIDENTIAL

Page 28/32

Statistical Analysis Plan 09 Nov 2022

jCyte, Inc Protocol No. JC02-2

S
4
3

jCyte, Inc Protocol No. JC02-2

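### No planned output counts how many eyes lose a prespecified number of letters, although the study's primary question is the safety of re-injection

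*SAP*

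**What the plan says.** The primary question is safety. SAP 13 puts it as "The primary endpoint of this study is to obtain safety profiles for reinjection of jCell". Protocol 3.2.2 lists the incidence and severity of treatment-emergent adverse events (TEAEs) and then "Safety visual assessments: slit lamp and fundus exam, IOP". Best corrected visual acuity (BCVA) is not in that list. Protocol 3.2.1 and SAP 10 place it among the secondary efficacy endpoints.

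For BCVA, SAP 11.1.1 says "BCVA will be analyzed using summary statistics of the average number of letters correct at each time point" and adds "Change from baseline will also be summarized using summary statistics for each post-baseline time point", with separate tables for the study eye and the non-study eye. SAP 6 says what these summaries contain: "Continuous variables will be summarized by presenting the number of observations, means, standard deviations (SDs), medians, minimums, and maximums". It also says "Individual subject data obtained from the eCRFs and any derived data will be presented by subject in data listings", and Appendix B includes a listing titled "Best Corrected Visual Acuity (E-ETDRS): Study Eye" (16.2.4.1.1) and its counterpart for the other eye (16.2.4.1.2).

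No table in SAP 11.1.1, SAP 13.3 or the Appendix B index counts eyes that lose a stated number of letters.

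**The concern.** Protocol 1.3 records that nobody had yet received a second injection in an eye already treated. Where both eyes were treated before, the better-seeing eye is preferred. Loss of acuity in that eye is a direct measure of harm, and BCVA is recorded in both eyes at every visit.

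SAP 5 justifies 25 to 30 subjects as enough to judge whether the safety profile matches that of earlier treatment. For vision loss, such a judgement needs a numerator and a denominator. SAP 13.3 gives counts and percentages for slit lamp, funduscopy, vitreous and OCT findings, but no incidence is planned for acuity.

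Timing matters too. SAP 6 treats any analysis done after database lock as post hoc and exploratory. A count taken later from the listings would have its cut-off chosen with the results in view.

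**Working it through.** **Inputs.** n = 25 and 30, one re-treated eye each (SAP 5). The planned statistics are those of SAP 6. The documents give no SD of change, no expected rate of loss and no letter threshold. The SD of 8 to 10 letters, the 20-letter example and the 10- and 15-letter cut-offs are therefore assumptions. There is no planned figure to reproduce, because the sample size rests on availability.

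**1. What the mean shows.** If k of n eyes lose L letters and the rest do not change, the mean shifts by -kL/n. For two eyes losing 20 letters:

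- n=25: -(2 × 20)/25 = -1.6 letters. SE = SD/√n runs from 8/√25 = 1.60 to 10/√25 = 2.00, so the shift is 0.8 to 1.0 SE.
- n=30: -(2 × 20)/30 = -1.33 letters. SE runs from 8/√30 = 1.46 to 10/√30 = 1.83, so the shift is 0.7 to 0.9 SE.

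The mean is insensitive to such losses.

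**2. What the minimum adds.** In the same example the minimum change at that visit is -20, so at least one of the two eyes shows. The minimum does not say how many eyes are near it. Nor does it say whether the worst eye at one visit is the worst eye at the next.

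**3. Can the full planned set of statistics tell one serious loss from three?** Two constructed sets of 25 changes:

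- A: -30, -15 twice, 2 eleven times, 3 ten times, 8 once.
- B: -30, -14, -7, -5, -2 four times, -1 twice, 0, 1, 2 twice, 3 twice, 4, 5 twice, 6 twice, 7 three times, 8.

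| | n | Mean | SD | Median | Min | Max | Eyes losing ≥15 |
|---|---|---|---|---|---|---|---|
| A | 25 | 0.0 | 8.03 | 2 | -30 | 8 | 3 |
| B | 25 | 0.0 | 8.07 | 2 | -30 | 8 | 1 |

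The planned table would be practically the same for both. B has one eye at -14, so at a 10-letter cut-off the counts are 3 and 2. That is a reason to report two cut-offs.

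**4. What a count would show.** Exact (Clopper-Pearson) limits for x eyes out of n are the 2.5% point of Beta(x, n-x+1) and the 97.5% point of Beta(x+1, n-x); for x = 0 the lower limit is 0.

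| Eyes with loss | n=25 | n=30 |
|---|---|---|
| 0 | 0% (0 to 13.7) | 0% (0 to 11.6) |
| 1 | 4.0% (0.1 to 20.4) | 3.3% (0.1 to 17.2) |
| 2 | 8.0% (1.0 to 26.0) | 6.7% (0.8 to 22.1) |
| 3 | 12.0% (2.5 to 31.2) | 10.0% (2.1 to 26.5) |

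If the true risk were 5%, the chance of seeing at least one such eye is 1 - 0.95^25 = 72% or 1 - 0.95^30 = 79%.

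**5. Do the adverse event tables fill the gap?** Under Protocol 8.1, marked or unforeseen worsening of RP is an adverse event. Progression that was to be expected is not, unless it is more severe than expected for that subject. No number of letters separates the two. The TEAE tables in SAP 13.2 and Appendix B are arranged by system organ class, preferred term, severity, relationship and seriousness. None is specified by eye, so they give no incidence for the treated eye beside its fellow.

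**The case against.** A reader might infer from the wording of SAP 11.1.1 that acuity is reported only as a mean, so that a serious loss is averaged away and cannot be seen. The documents do not support this. SAP 6 requires the median, minimum and maximum as well, and SAP 11.1.1 applies these summaries to change from baseline for each eye. The largest loss at each visit is therefore printed. The by-subject listings let anyone follow all 25 to 30 eyes through time, persistence included. The word average in that sentence may also refer to the two or three replicate measurements per eye that SAP 10.1.1 calls for at each visit.

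A reader might also infer that vision loss falls outside the adverse event definition. It does not. Protocol 8.1 includes marked or unforeseen worsening of RP, and Protocol 6.3.1 to 6.3.6 ask for changes in vision at every visit from Day 1 to Month 9. A serious loss has a route into the primary safety tables.

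All of this stands, and it limits the point to one of reporting. It does not remove the point, because the listings leave both the cut-off and the counting to the reader, and the adverse event route depends on case-by-case judgement.

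Three cautions about a count also stand. Scores stop at 0 letters (SAP 10.2, 10.3 and 11.1.1), so an eye that starts below 15 letters cannot lose 15. The seven-letter rule for a third measurement concerns replicates within one visit and does not validate a cut-off for change between visits. The non-study eye may itself have been treated earlier, and the better-seeing eye is preferred for re-treatment, so the non-study eye is not a clean control.

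**Conclusion.** The point holds as a gap in reporting. BCVA is planned as continuous summaries and listings within efficacy, and no count or proportion of eyes with a prespecified loss is planned as a safety output. The tables show the worst eye at each visit, but not how many re-injected eyes lost vision or whether the loss lasted.

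The planned statistics can be all but identical with one or three eyes losing at least 15 letters. The mean moves by about one SE or less when two eyes lose 20 letters. The first result rests on constructed data. The second rests on the assumed SD of 8 to 10 letters. The absence of a count rests only on the text of the SAP.

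The remedy has limits. With no losses at all, the upper 95% limit would still be 13.7% (n=25) or 11.6% (n=30), so the count describes the experience and cannot exclude a moderate risk.

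**What to change.** Before database lock, add to SAP 13.3 (or to Tables 14.2.1.1 and 14.2.1.2) the n (%) with exact 95% CI of eyes losing at least a prespecified number of letters from the SAP 10.2 baseline. Cut-offs of 10 and 15 letters are proposed; the documents set none, so the sponsor should justify the choice.

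- **Times:** each post-baseline visit, any post-baseline visit, and loss still present at the last visit. State how a loss first seen at the last visit is handled, since its persistence cannot be judged.
- **Eyes:** study and non-study eyes separately, the latter as descriptive context only.
- **Denominator:** eyes assessed whose baseline score is high enough to lose that many letters, with that number printed.

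If the database has already been locked, the same table can still be produced, labelled post hoc as SAP 6 requires.

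This is a cheap improvement: no new data, no change in sample size and no change to any planned analysis. The cost is table rows: two cut-offs × nine time points (seven visits, any, last) × two eyes = 36 proportions. The intervals will be wide, and the table will look less favourable if losses occur.
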